Appendix Figure 1. Stool Frequency and Rectal Bleeding Subscores Calculations at Screening

Appendix Table 1. Examples of Calculations for the Rectal Bleeding and the Stool Frequency Subscores of MCS and EBS at Baseline

Example	Diary Day Looking Back from Endoscopy Date							Anchor Day	Days for Calculation	Average Subscore	Final Subscore
	-7	-6	-5	-4	-3	-2	-1	E-Day 1			
	3 Jun	4 Jun	5 Jun	6 Jun	7 Jun	8 Jun	9 Jun	10 Jun			
Diary 1	M	M	2	M	1	2	X	X	2, 3, 5	1.67	2
Diary 2	M	M	M	M	0	1	X	X	2, 3	Missing	Missing
Diary 3	M	M	M	M	0	M	X	X	3	Missing	Missing
Diary 4	M	2	M	2	1	1	X	X	2, 3, 4	1.33	1

Days are named relative to Anchor Day Endoscopy Date (E Day 1), M Missing, X non evaluable
 The diary data collected on E Day 1 and E Day 1 will be discarded as endoscopy and its preparation may impact the validity of the diary data.

[figure not shown]
Calculation of Partial MCS at Baseline, and Postbaseline MCS, EBS, and Partial MCS

The calculation of baseline partial MCS and postbaseline MCS, EBS and partial MCS use the study visit date as the anchor date. For baseline pMCS, the visit date is the Day 1 visit. The calculations are as follows:

- 1) Subject diary data collected within 7 days prior to the visit day will be used for calculation, and some of the days within this 7-day window may be considered non-evaluable due to the endoscopy procedure and its preparation (ie, the day of the endoscopy and the day prior to the endoscopy).
- 2) The average of the 3 evaluable diary day entries within the 7-day window closest to the visit day (V-Day 1), rounded to the nearest integer, will be considered the stool frequency and rectal bleeding subscore for that visit
- 3) The PGA subscore used in the calculation of baseline partial MCS is the PGA subscore recorded on Day 1. At subsequent visits, the PGA subscore used in calculation of MCS and partial MCS is that recorded within the visit window
- 4) If there are 2 or less evaluable diary day entries for stool frequency or rectal bleeding within the 7-day window, no missing data imputation will be done. MCS, EBS and partial MCS will be considered as missing.
- 5) For MCS, if endoscopic subscore or PGA subscore is missing, MCS will be left as missing. For Partial MCS, if PGA is missing, partial MCS will be left as missing.

A schema of this approach and some examples are included below in [Appendix Figure 2](#) and [Appendix Table 2](#):

Appendix Figure 2. Stool Frequency and Rectal Bleeding Subscores Calculations at Baseline and Postbaseline

Appendix Table 2. Calculation of Partial MCS at Baseline, and Postbaseline MCS, EBS and Partial MCS

Example	Diary Day Looking Back from Visit Date							Anchor Day	Days for Calculation	Average Subscore	Final Subscore
	-7	-6	-5	-4	-3	-2	-1	V-Day 1			
	3 Jun	4 Jun	5 Jun	6 Jun	7 Jun	8 Jun	9 Jun	10 Jun			
Diary 1	E	X	3	M	M	M	0	X	-1, -5	Missing	Missing
Diary 2	4	4	X	E	X	3	3	X	-1, -2, -6	3.33	3
Diary 3	3	X	E	X	1	M	2	X	-1, -3, -7	2	2
Diary 4	2	3	4	4	X	E	X	X	-4, -5, -6	3.67	4
Diary 5	2	M	M	X	E	X	2	X	-1, -7	Missing	Missing
Diary 6	X	E	X	2	3	0	1	X	-1, -2, -3	1.33	1
Diary 7	M	3	X	E	X	M	M	X	-6	N/A	Missing

Days are named relative to Anchor Day (V Day 1 Visit Date), M Missing, X non evaluable, E Endoscopy Day

Sources of Information for Mayo Clinic Score Calculations

The sources of information used for the calculations of MCS and partial MCS are summarized in [Appendix Table 3](#) (the calculated MCS and partial MCS from ERT data will not be used for data analysis):

Appendix Table 3. Sources of Information for Calculating MCS and Partial MCS

Variable in Calculation	Data Source
Endoscopy Procedure Date	ENDODAT in ENDO dataset from CRF data for protocol-directed endoscopy; ENDODAT in MAYO dataset from ERT data for non-protocol-directed endoscopy
Visit Date	VISITDAT in VISDT dataset from CRF data
Stool Frequency Subscore	QSSTRESN in DIARY dataset with QSTESTCD="SF" from ERT data
Rectal Bleeding Subscore	QSSTRESN in DIARY dataset with QSTESTCD="RB" from ERT data
Physician Global Assessment	QSSTRESN in MAYO dataset with QSTESTCD="PGA" from ERT data
Endoscopic Score	MAYO in ENDO ROBERTS dataset from Robarts data

Note: Robarts is the vendor performing endoscopy central scoring;
 ERT is the vendor that electronically collects patient and investigator reported outcomes

Appendix 5. Study Treatment Failure Rules

Study treatment failure rules apply to treatment failure that occurs during the course of the study. Study treatment failure rules will be applied to all efficacy endpoints unless otherwise specified. All efficacy data will be censored (set to missing) after treatment failure criteria are met, regardless of the observed data. Subjects who do not have sufficient measurements after censoring to determine the dichotomized endpoint(s) will be considered non-responder for corresponding endpoint(s). Study treatment failure rules override other data handling rules.

Subjects who have any of the following events will be considered a study treatment failure after the earliest event through the end of the Induction Study (if the event occurred during induction) or through the end of the Maintenance Study (if the event occurred during maintenance), regardless of the actual efficacy data collected. Induction baseline will be referenced when calculating the potentially effective use for induction studies and maintenance baseline (re-baseline) will be referenced when calculating the potentially effective use for Maintenance Study.

1) Potentially effective steroid use

Potentially effective corticosteroids, for the purpose of this SAP, are steroids that may impact disease under study. **Potentially effective steroids** include the following steroids when administered for an indication of UC:

a) Commencement of:

Any steroid administered intramuscularly (IM), intravenously (IV), orally (PO), or rectally (PR) at any dose for 7 or more continuous days

- This rule applies regardless if a change in drug, dose, or route (from IM to IV to PO or PR or vice versa) occurs within the seven continuous days; and it includes oral steroids with intended local actions (eg, budesonide)
- b) Escalation of concomitant steroid dose above the baseline dose for 7 or more continuous days. The baseline steroid dose is defined as the dose at Day 1 of induction if the escalation occurs in the Induction Study, or Day 1 of maintenance (re-baseline) if the escalation occurs in the Maintenance Study. The prednisone equivalent dose will be used to determine escalation of concomitant systemic steroid dose even if there is a change in drug or route. For steroids with local actions (eg, budesonide or any rectally administered steroid), this rule will apply to scenarios where the post-baseline dose is above the baseline dose via the same drug and the same route for 7 or more continuous days.

Potentially effective steroid use only includes use of steroids administered via routes that are IM, PO, IV, or PR. The below steroids will **not** be considered potentially effective steroids regardless of indication for use:

- i) ocular steroids (ie, eye drops)
- ii) topical steroids (eg, cutaneously applied solely to the skin, or topically applied to the nasal mucosa)
- iii) inhaled steroids (eg, inhalational fluticasone for asthma)
- iv) intra-articular steroids (steroids administered directly into a joint)
- v) neuraxial steroids (steroids administered into the epidural or spinal space)

2) Potentially effective immunomodulator use

Commencement of a different class of oral, IM, SC, or IV immunomodulator drugs (where the subject was not previously taking concomitant immunomodulators of the same class on Day 1 of induction or maintenance), including but not limited to 6-MP, azathioprine, MTX, 6-thioguanine, and prohibited immunomodulators including but not limited to cyclosporine, leflunomide, tacrolimus, thalidomide regardless of dose, for 7 continuous days. The use of an immunomodulator will be considered potentially effective when it is administered for an indication of UC.

3) Potentially effective biologic agent use

Commencement of a biologic agent including but not limited to TNF α antagonists, IL-12/23 antagonists, and vedolizumab (or similar agents), regardless of indication for use and duration.

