disease. Ustekinumab (Stelara®, CNTO 1275; an IL-12 and IL-23 monoclonal antibody), upadacitinib (JAK inhibitor), etrolizumab (PRO145223; monoclonal antibody targeting the  $\beta 7$  subunit of the heterodimeric integrins  $\alpha 4\beta 7$  and  $\alpha E\beta 7$ ), risankizumab (IL-23 antibody) and ozanimod (RPC1063; selective S1P1 and S1P5 receptor agonist) are currently being tested in Phase 3 clinical trials. Tofacitinib, a JAK 1/3 inhibitor, was effective in a Phase 3 UC study {Sandborn 2017}. Leukocytapheresis therapy may be used in Japan {Fukunaga 2012}. Despite several classes of treatment options for patients with UC, there remains an unmet medical need, particularly in the treatment of moderately to severely active disease. Agents with novel mechanisms of action that target the inflammatory cascade, with oral dosing and acceptable immunomodulatory and hematologic effects, remain the most promising option to address these unmet needs.

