#### 3.5.2. Study Drug Discontinuation Considerations

The Gilead Medical Monitor should be consulted prior to study drug discontinuation when medically feasible.

Study drug must be permanently discontinued in the following instances:

- Any opportunistic infection
- Any serious infection that requires antimicrobial therapy or hospitalization, or any infection that meets SAE reporting criteria
- Febrile neutropenia (temperature  $> 38.3^{\circ}\text{C}$  or a sustained temperature of  $> 38^{\circ}\text{C}$  for more than one hour) with absolute neutrophil count of  $< 1,000/\text{mm}^3$
- Symptomatic anemia (eg, signs/symptoms including pallor, shortness of breath, new heart murmur, palpitations, lethargy, fatigue ) with hemoglobin  $< 7.5 \text{ g/dL}$  , or if transfusion is indicated regardless of hemoglobin value
- Complicated herpes zoster infection (with multi-dermatomal, disseminated, ophthalmic, or CNS involvement)
- Evidence of active HCV during the study, as evidenced by HCV RNA positivity
- Evidence of active HBV during the study, as evidenced by HBV DNA positivity

- Unacceptable toxicity or toxicity that, in the judgment of the investigator, compromises the subject's ability to continue study-specific procedures or is considered to not be in the subject's best interest
- Subject request to discontinue for any reason
- Subject noncompliance
- Pregnancy during the study; refer to Section 7.7.2.1
- Discontinuation of the study at the request of Gilead, a regulatory agency or an institutional review board or independent ethics committee (IRB/IEC)
- Subject use of prohibited concurrent therapy *may* trigger study drug discontinuation; consultation should be made with the Gilead Medical Monitor.
- Laboratory Criteria: After becoming aware of any of the below described abnormal laboratory changes occurring at any one time, an unscheduled visit (ie, sequential visit) should occur to retest within 3 to 7 days (except creatinine, which should be retested 7 to 14 days apart).

— 2 sequential neutrophil counts < 750 neutrophils/mm^3 (SI: < 0.75x10^9 cells/L)

— 2 sequential platelet counts < 75,000 platelets/mm^3 (SI: < 75.0x10^9 cells/L)

— 2 sequential aspartate aminotransferase (AST) or alanine aminotransferase (ALT) elevations > 3x the upper limit of normal (ULN) and at least one of the following confirmed values:

- total bilirubin >2x ULN

- INR > 1.5

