- 19) History of malignancy in the last 5 years except for subjects who have been successfully treated for non-melanoma skin cancer or cervical carcinoma in situ
- 20) History of lymphoproliferative disorder, lymphoma, leukemia, myeloproliferative disorder, or multiple myeloma
- 21) History of treatment with lymphocyte-depleting therapies, including but not limited to alemtuzumab, cyclophosphamide, total lymphoid irradiation, and rituximab
- 22) History of cytapheresis  $\leq$  2 months prior to screening
- 23) Use of prohibited concomitant medications as described in Section 5.4.2.
- 24) Any chronic medical condition (including, but not limited to, cardiac or pulmonary disease, or substance abuse) or psychiatric problem that, in the opinion of the Investigator or Sponsor, would make the subject unsuitable for the study or would prevent compliance with the study protocol procedures
- 25) Administration of a live or attenuated vaccine within 30 days of randomization
- 26) History of opportunistic infection or immunodeficiency syndrome
- 27) Currently on any chronic systemic (oral or intravenous) anti-infective therapy for chronic infection (such as pneumocystis (PCP), cytomegalovirus (CMV), herpes zoster, atypical mycobacteria)
- 28) History of disseminated *Staphylococcus aureus*
- 29) History of symptomatic herpes zoster or herpes simplex within 12 weeks of screening, or any history of disseminated herpes simplex, disseminated herpes zoster, ophthalmic zoster, or central nervous system zoster

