**Table 5-1. Prohibited Concomitant Medications**

Drug Class	Agents Disallowed	Prohibited Period
Strong P-gp Inducersa		
Anticonvulsants	Phenobarbital, phenytoin, carbamazepine	30 days prior to screening through the end of the study
Antimycobacterials	Rifabutin, rifapentine, rifampin	
Herbal/Natural Supplements	St. John's wort, danshen ( Salvia Miltiorrhiza )	
Prohibited IBD Medications		
Corticosteroids	Dose equivalent to > 30mg/day of prednisone	30 days prior to screening through the end of the study
TNF $\alpha$ antagonist	Infliximab, adalimumab, golimumab, certolizumab, or biosimilar agent	8 weeks prior to screening through the end of the study
Integrin antagonist	Vedolizumab and natalizumab	8 weeks prior to screening through the end of the study
Interleukin antagonist	Ustekinumab	12 weeks prior to screening through the end of the study
Rectal compounds	Rectal 5-ASA or rectal corticosteroids	2 weeks prior to screening through the end of the study
Antidiarrheal agents	Loperamide and diphenoxylate/atropine	2 weeks prior to screening through the end of the study
Other (non-biologic)	Cyclosporine, thalidomide, tacrolimus, leflunomide, and any investigational agent	30 days prior to screening through the end of the study
	Any JAK inhibitor	Any time before and through the end of the study
Investigational biologics	Any investigational biologic agent	8 weeks prior to screening through the end of the study (or at least 5 half-lives)
Lymphocyte-depleting therapies	Alemtuzumab, cyclophosphamide, total lymphoid irradiation, rituximab, and any other lymphocyte depleting therapy	Any time before and through the end of the study
Other Prohibited Medications		
Chronic Nonsteroidal Anti-inflammatory Drugs (NSAIDs) b	Aspirin, ibuprofen, naproxen, diclofenac, indomethacin, COX-2 inhibitors	From screening through the end of the study
Other biologics c	Antibody based or other systemic biologics, eg, denosumab, trastuzumab	Requires medical monitor consultation

a May decrease study drug exposure and are excluded to avoid potential reduction in study drug activity. PK results indicate filgotinib is a P-gp substrate, as a single dose of 200 mg itraconazole (a potent P-gp inhibitor) increased filgotinib Cmax by 64% and AUCinf by 45% and had no effect on the major, active metabolite GS-829845.

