3.1.3. Per-Protocol Analysis Sets

The Per-Protocol (PP) Analysis Set for each Induction Study (Cohort A Induction Study and Cohort B Induction Study) includes subjects in the respective FAS who meet the following criteria:

- Met the following key eligibility criteria:

Documented diagnosis of UC of at least 6 months AND with a minimum disease extent of 15 cm from the anal verge. Documentation should include endoscopic and histopathologic evidence of UC as follows:

- The criteria for documentation of UC based on endoscopy will be medical record documentation, or an ileocolonoscopy (full colonoscopy with the intubation of the terminal ileum) report dated ≥ 6 months before enrollment, which shows features consistent with UC, determined by the procedure performing physician
- The criteria for documentation of UC based on histopathology will be medical record documentation of or a histopathology report indicating features consistent with UC as determined by the pathologist

Moderately to severely active UC as determined by a centrally read endoscopy score ≥ 2 , a rectal bleeding score ≥ 1 , a stool frequency score ≥ 1 , and PGA of ≥ 2 as determined by the Mayo clinic scoring system with endoscopy occurring during screening; total score must be between 6 and 12, inclusive.

- Dosed at least 80% of both study drugs (filgotinib and PTM) while on-treatment (see Section 4.2.2) for the Induction Study
- Either had sufficient data to evaluate EBS remission at Week 10, or met treatment failure criteria for Week 10 EBS remission outcome
- Never exposed to any biologics listed in Appendix 2 for Cohort A Induction Study, or exposed to at least 1 of the biologics listed in Appendix 2 for Cohort B Induction Study

The PP Analysis Set for the Maintenance Study includes subjects in the FAS who meet the following criteria:

- Met the key eligibility criteria from Induction Study as stated above
- Dosed at least 80% of each study drug type while on-treatment (see Section 4.2.2) for Maintenance Study
- Met one of following 3 categories:

Had sufficient data to evaluate EBS remission outcome at Week 58, or

Met treatment failure criteria for Week 58 EBS remission outcome, or

Discontinued study drug due to protocol-specified disease worsening criterion

The PP Analysis Set is the secondary analysis set for efficacy analyses.

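### SAP Appendix 5 scores rectal steroids started for UC as treatment failure but leaves out rectal 5-ASA, which the protocol prohibits on the same table row

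*SAP*

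**What the plan says.** SAP Appendix 5 opens its list with "Subjects who have any of the following events will be considered a study treatment failure after the earliest event". Three kinds of event follow:

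1. Steroids given IM, IV, orally or rectally for UC, either started or raised above the baseline dose, for 7 or more continuous days.
2. A new class of oral, IM, SC or IV immunomodulator for UC, for 7 continuous days.
3. Any biologic agent.

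The open wording in items 2 and 3 extends those classes only. The reach of the list is wide: "Study treatment failure rules will be applied to all efficacy endpoints unless otherwise specified".

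Protocol Table 5-1 puts "Rectal 5-ASA or rectal corticosteroids" on one row of prohibited IBD medications, from 2 weeks before screening to the end of the study. Another row bars "Loperamide and diphenoxylate/atropine" for the same period. Cytapheresis appears only as an eligibility washout ("History of cytapheresis" within 2 months of screening, Protocol 4.2.2) and in the background ("Leukocytapheresis therapy may be used in Japan"). It is not in Table 5-1.

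Protocol 3.5.2 does not make prohibited use a mandatory reason to stop: it may "trigger study drug discontinuation; consultation should be made with the Gilead Medical Monitor". SAP 3.1.3 sets no concomitant-treatment criterion for the per-protocol set. Its outcome criterion for Induction is "Either had sufficient data to evaluate EBS remission at Week 10, or met treatment failure criteria for Week 10 EBS remission outcome".

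**The concern.** Rectal steroids and rectal 5-ASA are barred together, and Protocol 1.1 names topical mesalamine and topical steroids side by side as treatments for distal colitis. Scoring one as failure and ignoring the other needs a reason, and the documents give none. Remission reached with the help of rectal 5-ASA is then credited to the randomized arm.

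At Week 10 the error would carry forward. Week 10 EBS remission or MCS response decides entry to the Maintenance Study (Protocol 4.5.1) and membership of its FAS (SAP 3.1.2), and Week 10 EBS remission is half of the sustained EBS remission endpoint. At stake are a clear definition of the primary endpoint when a foreseeable prohibited treatment is used and, depending on which arm uses it more, either power or the size of the estimated effect.

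**Working it through.** **Can any rule other than Appendix 5 turn an evaluable rectal 5-ASA user into a non-responder?**

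- Non-responder imputation (SAP 6.1) acts only when measurements are insufficient. It does not apply.
- The per-protocol criteria (SAP 3.1.3) are key eligibility, 80% dosing, evaluable or failed, and biologic exposure. The user stays in as a responder.
- The sensitivity analyses (SAP 6.2.4.1 to 6.2.4.4) change the analysis set, the endoscopy reader, the handling of missing data, or the US/Korea males. None acts on concomitant treatment.
- Disease worsening (Protocol 3.6) requires discontinuation when worsening clinically requires a prohibited drug. SAP 6.1 counts such subjects as non-responders and SAP 6.2.4.3 keeps them so. This applies from Week 11 only and at investigator discretion.

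So Week 10 has no cover and Week 58 has partial cover.

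**Reproducing the stated power.** Inputs from Protocol 8.9: Induction 130 vs 260, 10% vs 25%; Maintenance 95 vs 190, 20% vs 40%; 2-sided 0.025 (z = 2.2414).

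Power = Φ[(Δ − c − z·SE0)/SE1], with SE0 pooled, SE1 unpooled, and c = 0 or c = ½(1/n1 + 1/n2).

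- Induction: pooled rate (13 + 65)/390 = 0.20, SE0 = 0.04297, SE1 = 0.03760.
  - c = 0: (0.15 − 2.2414 × 0.04297)/0.03760 = 1.428, giving 92.3%.
  - c = 0.00577: 1.275, giving 89.9%. The stated 90% is reproduced.
- Maintenance: pooled rate (19 + 76)/285 = 0.333, SE0 = 0.05923, SE1 = 0.05429.
  - c = 0: 1.238, giving 89.2%.
  - c = 0.00789: 1.093, giving 86.3%. This agrees with the stated figure of more than 85%.

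**If use adds false remitters.** The rate of use is an assumption. Here the planning rates are taken as the rates without the omitted treatment. Power is by exact enumeration of the pooled z-test for two binomials, at 0.02499 (Induction) and 0.025 (Maintenance).

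| Points of remission added | Induction | Maintenance |
|---|---|---|
| none | 92.8% | 89.4% |
| +1, placebo only | 87.6% | 85.3% |
| +2, placebo only | 80.5% | 80.4% |
| +3, placebo only | 71.9% | 74.7% |
| +1, both arms | 91.6% | 88.8% |
| +3, both arms | 89.0% | 87.6% |

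One point on placebo is about 1 of 130 subjects in Induction or 1 of 95 in Maintenance. If the extra point fell on filgotinib alone, the Induction difference would rise from 15 to 16 points, which inflates the effect.

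**Cost of scoring users as failures.** Here the planning rates are taken as the rates observed without the rule, and 10% of Induction remitters are assumed to be reclassified (normal approximation, c = 0, starting from 92.3%).

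- Both arms: 9.0% vs 22.5%, difference 13.5 points, power 88.1%.
- Placebo only: 9.0% vs 25%, difference 16.0 points, power 96.0%.
- Filgotinib only: 10% vs 22.5%, difference 12.5 points, power 80.6%.

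For Maintenance, 10% in both arms gives 18% vs 36%, and power falls from 89.2% to 83.4%.

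**The case against.** The other side has real points, and most of them limit how far the concern reaches.

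- **Week 58 is not wide open.** Protocol 3.6 requires discontinuation from blinded treatment when worsening needs a prohibited drug, and the SAP counts that as non-response. Many flaring subjects are therefore already handled. What remains is use without discontinuation, because the criterion rests on the investigator's judgement.
- **Use would be visible.** A reader might infer that no planned output would reveal it. SAP 7.4.2 summarises UC-specific concomitant medications by treatment group, and SAP 4.3 summarises important deviations by treatment group. An imbalance could be seen; what is missing is any effect on the endpoint.
- **Antidiarrhoeals cannot create remission.** EBS remission also needs a centrally read endoscopic subscore of 0 or 1 and a rectal bleeding subscore of 0. Loperamide can tip the stool item in someone who already meets the other two parts; it cannot make a responder of a subject in a flare.
- **JAK inhibitors are arguably covered.** The open wording of the immunomodulator rule names cyclosporine, leflunomide, tacrolimus and thalidomide, the same group of Table 5-1 in which JAK inhibitors sit. Naming them would only clarify.
- **Cytapheresis during the study is not addressed by the protocol.** That silence belongs to the protocol, and the documents show no on-study use.
- **Heavier use on placebo would be conservative.** In that case the omission costs power and offers no false-positive route. This is right as far as it goes, but the documents do not establish which arm would use more.

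None of this answers the rectal 5-ASA gap at Week 10.

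**Conclusion.** The point holds for rectal 5-ASA. Appendix 5 treats two products from one prohibited row differently, without explanation, and a Week 10 user who meets the EBS criteria is a responder in the primary and per-protocol analyses. At Week 58 the gap is partial.

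Size and direction are unknown, because no document gives a rate of use by arm. Under assumption, one point of contamination on placebo alone costs about 5 points of Induction power (92.8% to 87.6%); one point in both arms costs about 1 (to 91.6%). A reader might go further and infer a demonstrated bias towards filgotinib, or a demonstrated loss of power. The documents support neither: the first needs more use on filgotinib, the second more use on placebo. The finding is an undefined handling of a foreseeable event, and it is cheap to close.

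**What to change.** Make these changes before the study blind is broken. They concern analysis scoring only and leave patient management as it is.

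1. **SAP Appendix 5:** add a rule that starting rectal 5-ASA for UC, for 7 or more continuous days, is study treatment failure from that date, in both Induction and Maintenance, parallel to the rectal steroid rule. The per-protocol set follows without further change, because it keeps subjects who met failure criteria.
2. **SAP 6.2.4:** add one sensitivity analysis of EBS remission that scores as non-responders all subjects with recorded antidiarrhoeal use in the diary scoring window or any on-study cytapheresis. Report use by arm.
3. **Do not make antidiarrhoeal diary days non-evaluable.** Appendix 4 uses a 7-day window and may already drop three days around endoscopy. That leaves four, so two antidiarrhoeal days would leave two, below the three required. The subject would then be missing instead of failed: a non-responder in the primary analysis, a success in missing-data analysis 2, a success in analysis 3 if on placebo, and outside the per-protocol set.
4. **Optional:** name JAK inhibitors other than study drug in the immunomodulator rule, as clarification.

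The cost is SAP wording and one derivation from the concomitant-medication eCRF, where Protocol 5.4 already requires all medications to be recorded. A few more subjects in either arm become non-responders and observed rates may fall slightly. If 10% of remitters in both arms were reclassified, Induction power would fall by about 4 points (92.3% to 88.1%) and Maintenance power by about 6 (89.2% to 83.4%); rarer use would cost less. Subjects who become Week 10 failures would also leave the Maintenance FAS as SAP 3.1.2 defines it. That exclusion rests on events before re-randomization, so it does not disturb the comparison of arms.
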